RECIST	Response Evaluation Criteria in Solid Tumors
SAP	Statistical Analysis Plan
SD	Stable Disease
SOC	System Organ Class
TFLs	Tables, Figures, Listings
WHO	World Health Organization

1 Introduction

This statistical analysis plan (SAP) describes all planned analyses for the final Clinical Study Report (CSR) of study 200104 (DRB436B2205), a phase IIA, open label, multi-center study to investigate the objective response rate of Dabrafenib in combination with Trametinib in subjects with BRAF V600 mutation-positive melanoma.

The previous SAP for primary analysis was finalized on 06-Apr-2018, which described all planned analyses for the primary CSR. Based on the results in the primary CSR, dabrafenib and trametinib combination was approved in People's Republic of China (PRC).

This SAP is for the final analysis, i.e., the study closeout SAP. The content of this SAP is based on protocol DRB436B2205 Amendment v08. All decisions regarding final analysis, as defined in the SAP document, have been made prior to database lock of the study data.

1.1 Study design

This is a single-arm, Phase IIA, open-label, multi-center study evaluating safety and efficacy of dabrafenib and trametinib combination therapy in BRAF V600 mutant-positive melanoma.

Approximately 65 subjects were enrolled in the study.

Overall response rate (ORR), as assessed by local investigators review of tumor response and using RECIST 1.1 criteria, is the primary endpoint in this study.

The primary analysis was performed after all subjects had been followed for at least 16 weeks or had at least 2 tumor assessments or had discontinued study, with a data cut-off on 23-Feb-2018.

Treatment will continue until disease progression, death, unacceptable toxicity, or withdrawal of consent, or study completion. After treatment discontinuation, subjects will be followed for survival and disease progression as applicable.

Survival and new anti-cancer therapy follow-up will continue until study completion. The study completion is defined as:

- In case all subjects stop study treatment within 48 weeks after Last Subject First Visit (LSFV): the study is completed once the last subject has completed the 48 weeks survival follow-up or all subjects die or loss to follow-up, whichever comes first.
- In case some subjects are still on study treatment 48 weeks after LSFV: the study is completed once all subjects stop study medication, or all subjects who are still on study medication can have access to alternative supply of MEK/BRAF inhibitors, whichever comes first.

Doses of study treatment may be modified and/or interrupted for management of toxicities associated with study treatment.

No formal interim efficacy analysis is planned for this study.

1.2 Study objectives and endpoints

Table 1-1 Study Objectives and Endpoints

Objectives	Endpoints
Primary	

 To determine the objective response rate (ORR) of dabrafenib in combination with trametinib in subjects with BRAF V600 mutation-positive, unresectable or metastatic acral lentiginous or cutaneous melanoma 	
 ORR is defined as the percentage of subjects with evidence of a confirmed complete response (CR) or partial response (PR) as per RECIST v1.1 [Eisenhauer, 2009].
Secondary	

 To further evaluate the antitumor activity (progression-free survival (PFS), duration of response (DOR), and overall survival (OS)) 	
 PFS is defined as the time from first dose of study treatment until the first date of either objective disease progression or death due to any cause. Duration of response is defined as the time from first documented evidence of CR or PR until the earliest date of documented radiological progression or death due to any cause among subjects who achieved a confirmed CR or PR. OS is defined as the interval from first dose of study treatment to the date of death, irrespective of the cause of death; subjects still alive will be censored at the date of the last contact.

Objectives	Endpoints

 To assess exposures to dabrafenib, dabrafenib metabolites, and trametinib after a single dose and at steady-state, and characterize the population pharmacokinetics and pharmacodynamics of dabrafenib and trametinib 	
 Trametinib, dabrafenib and dabrafenib metabolites concentrations by visit. For Mainland Chinese subjects with day 1 or day 15 samples, noncompartmental PK parameters include trametinib, dabrafenib and dabrafenib metabolites C_{max}, t_{max}, C_τ, AUC(0-t), and AUC(0-8); AUC(0-12) (dabrafenib and dabrafenib metabolites only), AUC (0-24) (trametinib only) and the dabrafenib metabolite to dabrafenib ratio of AUC(0-t), the accumulation ratio calculating by using the pharmacokinetic parameters from Day 1 or Day 15 need to be provided. Population PK parameters include, apparent clearance following oral dosing (CL/F), volume of distribution (V/F), and absorption rate constant (K_a) for dabrafenib and trametinib.

 To evaluate the safety and tolerability of dabrafenib and trametinib 	
 Safety as measured by clinical assessments including vital signs and physical examinations, 12-lead electrocardiograms (ECG), echocardiogram (ECHO), eye exams, chemistry and hematology laboratory values, and adverse events (AEs).

[REDACTED]
 
[REDACTED]
	
[REDACTED]
 
[REDACTED]

Objectives	Endpoints

 • [REDACTED] 	
 • [REDACTED]

 • [REDACTED] 	
 • [REDACTED]

2 Statistical methods

2.1 Data analysis general information

SAS version 9.4 software will be used to perform all data analyses and to generate tables, figures and listings.

Data will be summarized following Novartis outputs shells, however data model will follow GSK legacy data (IDSL).

2.1.1 Data included in the analysis

The Last Patient Last Visit (LPLV) date of the study is 19-Apr-2021, which will be used for final reporting (See section 1.1 for the definition of study completion).

Logically, all data collected in the database should be included in the final analysis and there should be no data cut-off. However, for Mainland Chinese patients, due to local regulations in China (lack of HGRAC approval), data from 01-Jul-2019 (inclusive) onwards can not be used, so there is a specific data cut-off of 30-Jun-2019 applied for these patients in this final analysis. For non Mainland Chinese patients, there is no data cut-off applied, i.e., all statistical analyses will be performed using all data collected in the database for these patients. All data with an assessment date or event start date (e.g. vital sign assessment date or start date of an adverse event) prior to or on the cut-off date will be included in the analysis. Any data collected beyond the cut-off date will not be included in the analysis and will not be used for any derivations.

All events with start date before or on the cut-off date and end date after the cut-off date will be reported as “ongoing”. Events starting before or on the cut-off date and not having documented end date will be reported as “ongoing”. This approach applies, in particular, to adverse event and concomitant medication reports. For these events, the end date will not be imputed and therefore will not appear in the listings.

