XRT	Radiation therapy

PROTOCOL SUMMARY

Rationale

Cutaneous melanoma is the most aggressive form of all skin cancers. Historically, the median survival time for subjects with Stage IV melanoma has been approximately 6 months and a median time to progression-free survival (PFS) at 1.7 months [Korn EL, 2008].

Dependence on MAPK signaling is a key feature of BRAF V600 mutant melanoma, as demonstrated by the clinical efficacy of vemurafenib, dabrafenib, and trametinib Phase III results [Chapman PB, 2011; Hauschild A 2012; Flaherty KT, 2012b]. While monotherapy with MAPK inhibitors represents a significant advance in the treatment of BRAF V600 mutation-positive, unresectable or metastatic melanoma, approximately half of patients treated with a BRAF or MEK inhibitor as monotherapy will develop resistance and progress within 5 to 7 months of starting treatment [Sosman JA, 2012; Hauschild A, 2012; Flaherty KT, 2012a]. Concomitant inhibition of BRAF and MEK may lead to greater response rates, provide more durable responses, and increase progression free survival and overall survival. Furthermore, hyperproliferative skin lesions, including cuSCC and keratoacanthoma, have been associated with paradoxical activation of the MAPK pathway by BRAF inhibition.

Much has changed in the treatment landscape of melanoma since the past 5 years. The immunotherapy as anti-cancer treatment in melanoma has significantly advanced. Ipilimumab, a monoclonal antibody that blocks cytotoxic T-lymphocyte antigen or CTLA-4, was approved by the US-Food and Drug Administration (FDA) for unresectable or metastatic melanoma in 2011. 2 immune check-point therapy, Programmed Death (PD) receptor-1 antibody (pembrolizumab and nivolumab) were also approved in 2014 for the treatment of metastatic melanoma following the standard treatment. The combination of ipilimumab and nivolumab also received FDA approval as first line treatment for metastatic melanoma in September, 2015 for BRAF wild-type patients, and extended to BRAF mutation patients in January 2016. However these medicines are not readily accessible in some countries, such as China.

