2.1.2 General analysis conventions

Pooling of centers: Unless specified otherwise, data from all study centers will be pooled for the analysis. Due to expected small number of subjects enrolled at centers, no center effect will be assessed.

Qualitative data (e.g., gender, race, etc.) will be summarized by means of contingency tables by Mainland Chinese and all subjects; a missing category will be included as applicable. Percentages will be calculated using the number of subjects in the relevant population or subgroup as the denominator.

Quantitative data (e.g., age, body weight, etc.) will be summarized by appropriate descriptive statistics (i.e. mean, standard deviation, median, minimum, and maximum) by Mainland Chinese and all subjects.

Mainland Chinese population means the subjects enrolled from mainland China. All subjects means all subjects enrolled to the study.

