2.7.2 Statistical hypothesis, model, and method of analysis

Similar to the analysis of primary endpoint, there is no formal hypothesis testing. PFS, OS and DOR will be summarized descriptively using Kaplan-Meier medians and quartiles.

Since there is a single primary endpoint (ORR), supported by secondary endpoints, the nominal level of significance for the primary analysis will not be affected by multiplicity.

PFS based on local investigators review of tumor assessments and using RECIST 1.1 criteria is a secondary endpoint in this trial and will be analyzed using the same conventions as that of the primary efficacy analysis. The distribution of PFS will be estimated using the Kaplan-Meier method. The median PFS along with 95% confidence intervals will be presented.

The survival distribution of OS distribution will be estimated using the Kaplan-Meier method, and Kaplan-Meier curves, medians and 95% confidence intervals [Brookmeyer and Crowley 1982] of the medians intervals.

DOR will be listed and summarized for all subjects in the FAS with confirmed CR or PR. The distribution of duration of response will be estimated using the Kaplan-Meier method and the median duration of response will be presented along with 95% confidence interval only if a sufficient number of responses is observed.

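### Overall survival is pooled across two regional data cut-offs up to 659 days apart, so the late part of the Kaplan-Meier curve falls only through non-Mainland deaths; regional curves should be added

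*SAP*

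**What the plan says.** SAP 2.1.1 sets two rules. For Mainland Chinese subjects, data from July 2019 onwards cannot be used because Human Genetic Resource Administration of China (HGRAC) approval is lacking, "so there is a specific data cut-off of 30-Jun-2019 applied for these patients in this final analysis". For everyone else, "For non Mainland Chinese patients, there is no data cut-off applied". The end of data elsewhere is bounded by the end of the study: "The Last Patient Last Visit (LPLV) date of the study is 19-Apr-2021". The restriction on Mainland data is complete: "Any data collected beyond the cut-off date will not be included in the analysis and will not be used for any derivations". SAP 4 lists it as a change to the protocol analysis.

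The two regions are then combined. Under SAP 2.1.2, "data from all study centers will be pooled for the analysis". SAP 2.7.2 states: "The survival distribution of OS distribution will be estimated using the Kaplan-Meier method". SAP 5.4.2 adds survival estimates with confidence intervals at chosen time points. The axis is time from first dose (SAP 2.7.1), not calendar time.

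SAP 2.1.2 provides a regional display for categorical data, which "will be summarized by means of contingency tables by Mainland Chinese and all subjects", and the same for continuous data. It does not mention Kaplan-Meier output. SAP 2.2.3 (subgroups) is marked not applicable, and SAP 2.7 plans no time-to-event analysis by region or at a common cut-off. SAP 2.7.1 still speaks of a single cut-off for each OS analysis, which does not match the two rules in SAP 2.1.1.

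**The concern.** Kaplan-Meier estimation assumes that a censored subject has the same future risk as those still followed. Here administrative censoring is set by region. If region is related to survival, Mainland subjects censored at June 2019 are in effect given the later hazard of non-Mainland subjects. The pooled late curve then estimates neither the whole trial population nor either region.

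A regional difference in OS is plausible, not shown. The Protocol Summary says of immune checkpoint drugs: "However these medicines are not readily accessible in some countries, such as China". Protocol 6.3 lets subjects receive other anti-cancer therapy after study treatment. That treatment after progression differed between the participating regions is an inference from these two statements; the protocol does not say so.

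At stake are the late OS rates and any late quartile. The primary endpoint, objective response rate, does not depend on this.

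**Working it through.** The documents give no OS target, event count or number at risk, so there is no planned figure to reproduce. The check is date arithmetic followed by a large-sample calculation under stated assumptions.

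**1. Gap between the cut-offs.** 30-Jun-2019 to 19-Apr-2021 is 659 days. With the SAP month of 30.4375 days, 659 / 30.4375 = 21.7 months. This is a maximum, because the region of the last patient is not stated.

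**2. When regional censoring starts.** SAP 1.1 puts the primary cut-off at 23-Feb-2018, with at least 16 weeks of follow-up as one of its triggers. Sixteen weeks earlier is 3-Nov-2017, taken as an approximate latest first dose.
- Minimum potential Mainland follow-up: 604 days / 30.4375 = 19.8 months.
- Minimum potential non-Mainland follow-up: 1263 days / 30.4375 = 41.5 months.

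OS is censored at last contact, and contacts after treatment are every 12 weeks ± 7 days. Mainland censoring could therefore begin up to 13 weeks (3.0 months) earlier, at about 17 months.

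**3. When Mainland subjects leave the risk set.** First-dose dates by region are not given. Three amendment dates serve as assumed Mainland starts:

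| Assumed first Mainland dose | Days to 30-Jun-2019 | Longest Mainland follow-up |
|---|---|---|
| 25-Oct-2016 (Amendment 4) | 978 | 32.1 months |
| 04-Mar-2016 (Amendment 3) | 1213 | 39.9 months |
| 27-Mar-2015 (Amendment 1) | 1556 | 51.1 months |

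As an illustration, take 65 subjects with a 75% Mainland share and uniform accrual, non-Mainland accrual starting 27-Mar-2015. Assume exponential survival matching the 72% 12-month rate in Protocol 1.4.1, that is, a median of 12 × ln 2 / −ln 0.72 = 25.3 months. The expected numbers at risk at 36 months (Mainland / non-Mainland) are 0 / 6.1, 3.5 / 6.1 and 8.8 / 6.1 for the three starts.

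**4. Bias of the pooled curve.** With share w, survival S and probability G of remaining uncensored in each region, the pooled Kaplan-Meier curve tends to exp(−∫h*), where h*(t) = Σ w S G h / Σ w S G. The target is the mixture Σ w S(t). Assumptions: exponential survival, non-Mainland median 30 months, Mainland share 40% to 77%, and Mainland censoring uniform from 19.8 months to the longest Mainland follow-up. Pooled minus mixture at 42 months, in percentage points:

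| Longest Mainland follow-up | HR 1 | HR 1.25 | HR 2 |
|---|---|---|---|
| 32 months | 0 | +1.1 to +1.9 | +2.5 to +4.3 |
| 39.9 months | 0 | +0.8 to +1.1 | +1.7 to +2.6 |
| 51.1 months | 0 | +0.4 to +0.5 | +1.0 to +1.3 |

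At 36 months, with 32 months of Mainland follow-up, the bias is +0.8 to +1.2 (HR 1.25) and +1.9 to +3.0 (HR 2). At 24 months it is at most 0.2 in every case.

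**5. What the late curve represents.** Take a 50% share, medians of 18 (Mainland) and 30 months (non-Mainland), and Mainland start 25-Oct-2016. At 40 months the mixture is 0.5 × 2^(−40/18) + 0.5 × 2^(−40/30) = 0.5 × 0.214 + 0.5 × 0.397 = 0.306. The pooled curve tends to 0.329, between the mixture and the non-Mainland value of 0.397. With the medians exchanged, the pooled curve tends to 0.272 against 0.306, so the sign reverses.

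**6. Sampling error.** For a survival rate near 40% with 65 subjects and no censoring, the standard error is √(0.4 × 0.6 / 65) = 0.061. In the case with the largest bias (HR 2, 77% share) the mixture at 42 months is 0.77 × 2^(−42/15) + 0.23 × 2^(−42/30) = 0.198, and √(0.198 × 0.802 / 65) = 0.049. Censoring makes both larger.

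**The case against.** The restriction is regulatory, is disclosed twice, and is not an error. OS is a secondary, descriptive endpoint with no test. The bias is zero if survival is equal across regions and below one standard error in every scenario computed. The hazard ratio, medians, Mainland share and accrual dates are all assumed. All of this stands, and it limits the weight of the point.

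Four stronger readings are tempting, and the documents do not support them.
- *The late curve describes only non-Mainland subjects.* Only its later drops do. Its level still carries all earlier Mainland survival, as step 5 shows.
- *No Mainland subject is at risk after 32 months.* That rests on one assumed start date; 32 to 51 months is the range. A later tail made up of Mainland subjects is not strictly excluded. It would need the first non-Mainland dose to come at least 659 days after the first Mainland dose, hence Mainland dosing before about 14-Jan-2016, which is unlikely.
- *PFS and duration of response are equally affected.* The median PFS values that the protocol cites for the combination (9.3 and 11.4 months) fall before regional censoring starts, PFS is censored at new anti-cancer therapy, and access to later treatment gives no reason for a regional PFS difference.
- *One common cut-off of 30-Jun-2019 would cure the problem.* It aligns calendar time, not time from first dose. If Mainland accrual started in October 2016 and accrual elsewhere in March 2015, the 42-month bias at HR 2 and a 77% share falls only from +4.3 to about +4.0 points, while up to 659 days of non-Mainland follow-up are dropped.

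The objection does not remove the gap in the plan. Even if the Mainland and all-subjects display were extended to survival curves, it would give no non-Mainland curve, and the all-subjects curve would still mix the two cut-offs.

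**Conclusion.** The point holds in a limited form. Censoring in the pooled OS analysis depends on region by design, and nothing planned lets a reader see this. Up to about 17 to 20 months the regional rule hardly matters. From there to about 32 to 51 months the Mainland contribution shrinks, and after that the pooled curve falls only through non-Mainland deaths.

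The late bias is about +0.4 to +4.3 points at 42 months for an assumed Mainland hazard ratio of 1.25 to 2, on the exponential and accrual assumptions above. It is zero at a ratio of 1 and negative below 1. The documents do not show which case applies. A reader might infer that the reported OS is too favourable; they do not support that. The conclusion is that late pooled OS rates have no clear population, not that they are known to be wrong. The point is worth considering and does not bear on the primary endpoint.

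**What to change.** 1. In SAP 2.7.2, add Kaplan-Meier OS curves and time-point estimates for Mainland and non-Mainland subjects separately, each with its own available follow-up and with numbers at risk by region. Within each region the administrative cut-off then no longer depends on region.
2. State that pooled OS rates beyond the longest Mainland follow-up will not be interpreted, and report that follow-up time.
3. Reconcile the single cut-off wording in SAP 2.7.1 with the two rules in SAP 2.1.1.
4. Optionally, add a pooled analysis at a common 30-Jun-2019 cut-off as a sensitivity analysis. It should not replace the analysis with full follow-up.

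The cost is SAP wording and a few extra outputs from existing programs. No Mainland data after June 2019 are needed. The drawback is small regional numbers and therefore wide intervals.

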2.1.2 General analysis conventions

Pooling of centers: Unless specified otherwise, data from all study centers will be pooled for the analysis. Due to expected small number of subjects enrolled at centers, no center effect will be assessed.

Qualitative data (e.g., gender, race, etc.) will be summarized by means of contingency tables by Mainland Chinese and all subjects; a missing category will be included as applicable. Percentages will be calculated using the number of subjects in the relevant population or subgroup as the denominator.

Quantitative data (e.g., age, body weight, etc.) will be summarized by appropriate descriptive statistics (i.e. mean, standard deviation, median, minimum, and maximum) by Mainland Chinese and all subjects.

Mainland Chinese population means the subjects enrolled from mainland China. All subjects means all subjects enrolled to the study.

2.1.3 General definitions

2.1.3.1 Study drug and study treatment

Study drug and study treatment both refer to Dabrafenib in Combination with Trametinib.

2.1.3.2 Date of first/last administration of study drug

The date of first administration of study drug is defined as the first date when a non-zero dose of study drug is administered and recorded on the exposure form. For the sake of simplicity, the date of first administration of study drug will also be referred as start date of study drug.

The date of last administration of study drug is defined as the last date when a non-zero dose of study drug is administered and recorded on the exposure form. This date is also referred as last date of study drug.

2.1.3.3 Study day

The study day for all assessments (e.g. tumor assessment, death, disease progression, tumor response, performance status, adverse event onset, laboratory abnormality occurrence, vital sign measurement, dose interruption) will be calculated using the start date of study drug as the origin. For assessments occurring after or on the start date of study drug, study day will be calculated as:

$$\text{Study Day} = \text{Event date} - \text{start date of study drug} + 1.$$

The first day of study drug is therefore study day 1.

For any assessment or events such as baseline disease characteristics or medical history (e.g., time since diagnosis of disease) occurring prior to the start of the study drug, study day will be negative and will be calculated as:

$$\text{Study Day} = \text{Event date} - \text{start date of study drug}.$$

The study day will be displayed in the data listings.

2.1.3.4 Time unit

A year length is defined as 365.25 days. A month length is 30.4375 days (365.25/12). If duration is reported in months, duration in days will be divided by 30.4375. If duration is reported in years, duration in days will be divided by 365.25.

